**Protocol: GHLIP-2-001**

**Study Sponsor: Golden Biotechnology Corporation**

AE. Only AEs beginning at or after the beginning of study drug administration will be included.

Similarly, counts of AEs by strongest relationship to study drug will be presented.

A data listing will also be presented showing all AEs, which started prior to the administration of any study drug.

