3.4. Safety Endpoints

Safety endpoints include the compliance and tolerability of the study drug, incidence of treatment emergent adverse events, safety laboratory values, vital signs, physical examinations, ECG, and the frequency and severity of muscle symptoms at each scheduled visit.

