6.2.2. Enrollment/Randomization (Day 1)

Randomization Assessments at Visit 2

Once a patient has fulfilled the entry criteria, he/she will be randomized into either Antroquinonol 150 mg, Antroquinonol 100 mg, Antroquinonol 50 mg or placebo treatment group using a permuted block randomization method with 1: 1: 1: 1 ratio. The subject will be registered with a randomization number, and the study drug will be administered. The importance of compliance with study drug should be emphasized.

The assessments listed below will be performed. If the eligibility is confirmed and a wash-out period is not needed for the subject, based on investigator's judgements, the blood test, CT Scan, and Doppler color flow mapping required at visit 2 can be replaced by data obtained 14 days before V2.

- Physical examination
- Anthropometric measures (Height, weight, waist circumference, BMI)
- Vital signs (pulse rate, body temperature, respiratory rate, and blood pressure)

- Blood samples for
 - lipid profile (total cholesterol, TG, HDL-C, LDL-C and HDL-C /LDL-C ratio)
 - hematology (WBC, RBC, Hb, Hct, RDW, platelet, MCV, MCH, MCHC, neutrophil-band and segment, lymphocyte, monocyte, eosinophil, basophil)
 - serum chemistry (AST, ALT, CPK, BUN, serum creatinine, albumin, total bilirubin, direct bilirubin, ALP, total protein)
 - biomarkers (hsCRP, IL-1, IL-6, and TNF-alpha)
- 12-lead electrocardiogram
- Brachial-ankle pulse wave velocity (baPWV) and ankle-brachial index (ABI)
- Doppler color flow mapping, and CT scan of the liver
- Urinalysis
 - routine urine test (pH, protein, glucose, ketone, blood, urobilinogen, bilirubin, nitrite, leukocyte)
 - clinical microscopy

In addition, information on adverse events during the wash-out period and new concomitant medications will be collected.

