8. ASSESSMENT OF SAFETY

8.1. Adverse Events (AE)

An adverse event is any untoward or unfavorable medical occurrence in a human subject, including any abnormal sign (for example, abnormal physical exam or laboratory finding), symptom, or disease, temporally associated with the subject's participation in the research, whether or not considered related to the subject's participation in the research.

All AEs including local and systemic reactions not meeting the criteria for "serious adverse events" will be captured on the appropriate AE page of CRF. Information to be collected includes event description, time of onset, clinician's assessment of severity, relationship to study product (assessed only by those with the training and authority to make a diagnosis) and time of resolution/stabilization of the event. All AEs occurring while on study must be documented appropriately regardless of relationship. All AEs will be followed to adequate resolution which means subjects experiencing AEs shall be followed until recovery, recovery with residual effects, continuing, death or lost to follow-up and be recorded on CRF AE page.

Pre-existing conditions will be recorded as baseline on the "Medical History" of CRF. If the pre-existing condition does not change, it does not have to be reported as an AE on subsequent cycles. However, if it deteriorates at any time during the study, it will be recorded as an AE.

All AEs must be graded for **severity** and **relationship** to study product. The adverse event toxicity grading scale used will be the CTCAE v4.03 grading score.

Severity of AEs

All AEs will be assessed by the clinician using a protocol defined grading system. For events not included in the protocol defined grading system, the following guidelines will be used to quantify intensity.

Grade 1	Mild; asymptomatic or mild symptoms; clinical or diagnostic observations only; intervention not indicated.
Grade 2	Moderate; minimal, local or noninvasive intervention indicated; limiting age-appropriate instrumental ADL.
Grade 3	Severe or medically significant but not immediately life-threatening; hospitalization or prolongation of hospitalization indicated; disabling; limiting self care ADL.
Grade 4	Life-threatening consequences; urgent intervention indicated
Grade 5	Death related to AE.

ADL: activities of Daily Living

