Changes in the severity of an AE will be documented to allow an assessment of the duration of the event at each level of intensity to be performed. Adverse events characterized as intermittent require documentation of onset and duration of each episode.

Relationship to Study Drugs

The clinician's assessment of an AE's relationship to test article (study drug) is part of the documentation process, but it is not a factor in determining what is or is not reported in the study. If there is any doubt as to whether a clinical observation is an AE, the event will be reported. All AEs must have their relationship to study product assessed using the terms defined as follows. In a clinical trial, the study product must always be suspect. To help assess, the following guidelines are used.

Causality

- **Certain:** There is clear evidence to suggest a causal relationship, and other possible contributing factors can be ruled out. The clinical event, including an abnormal laboratory test result, occurs within a reasonable timeframe after study procedure(s) and cannot be explained by concurrent disease or other drugs or chemicals.
- **Probable:** There is evidence to suggest a causal relationship, and the influence of other factors is unlikely. The clinical event, including an abnormal laboratory test result, occurs within a reasonable time after study procedure(s), is unlikely to be attributed to concurrent disease or other drugs or chemicals, and follows a clinically reasonable response to study events.
- **Possible:** There is some evidence to suggest a causal relationship (e.g., the event occurred within a reasonable time after study procedure(s)). However, the influence of other factors may have contributed to the event (e.g., the subject's clinical condition, other concomitant events). Although an adverse event may be judged only as "possibly related" soon after discovery, it can be flagged as requiring more information and later be upgraded to "probably related" or "definitely related", as appropriate.
- **Unlikely:** A clinical event, including an abnormal laboratory test result, whose temporal relationship to study procedure(s) makes a causal relationship improbable (e.g., the event did not occur within a reasonable time after study procedure(s)) and in which other drugs or chemicals or underlying disease provides plausible explanations (e.g., the participant's clinical condition, other concomitant treatments).

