### **10.1.1 All Adverse Events**

Summaries of incidence rates (frequencies and percentages), intensity, and relationship to study drug of individual AEs by System Organ Class and Preferred Term (MedDRA) will be prepared. Each patient will be counted only once within each preferred term per study period. If a patient experiences more than one AE within a prepared item for the same recording period, only the AE with the strongest relationship or the greatest intensity, as appropriate, will be included in the summaries of relationship and intensity.

Summaries will be presented by treatment group for Antroquinonol. Fisher's exact test will be used to compare rates for System Organ Classes across treatment groups. A similar summary by treatment group will be presented for all patients in the Safety Population.

Counts of AEs by maximum intensity will be presented for patients in the Safety Population by treatment group, grouped by the treatment the patient had received most recently prior to the

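### SAP 10.1.1 selects adverse events for the intensity and relationship counts by onset date alone, so an event that starts in wash-out and worsens on study drug can be left out of both

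*SAP*

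**What the plan says.** SAP 10.1.1 describes two sets of counts that concern this point. The first is introduced with "Counts of AEs by maximum intensity will be presented for patients in the Safety Population by treatment group", and its paragraph closes with the inclusion rule "Only AEs beginning at or after the beginning of study drug administration will be included". The second follows at once: "Similarly, counts of AEs by strongest relationship to study drug will be presented". Events that began before dosing are handled separately: "A data listing will also be presented showing all AEs, which started prior to the administration of any study drug".

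The protocol supplies the data to which these rules apply:

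- Section 3.4 names as a safety endpoint the "incidence of treatment emergent adverse events". Neither document defines the term. SAP 3.2.3 lists only an analysis of adverse events, and SAP 12 states that nothing in the protocol's analysis has changed.
- Section 6.2.2 (Visit 2) says that "information on adverse events during the wash-out period and new concomitant medications will be collected".
- Section 8.1 says of a pre-existing condition that "if it deteriorates at any time during the study, it will be recorded as an AE". It also says, of AEs in general, "Changes in the severity of an AE will be documented", so that the time spent at each level of intensity can be assessed.

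**The concern.** An AE is usually called treatment-emergent if it starts on treatment or if it was already present and gets worse on treatment. The SAP rule covers only the first half. The protocol deliberately collects events before the first dose, so the second half can arise in this trial.

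The two tables concerned describe how severe the on-drug events were and how strongly they were attributed to the drug. If a mild wash-out symptom becomes more severe after dosing and is filtered out on its onset date, its worst on-drug grade and its causality assessment are both missing from those tables. Safety and tolerability is a stated secondary objective (Protocol 2.2). The expected reactions in Protocol 8.2 are diarrhea, vomiting and nausea, common symptoms that a patient could also have before dosing.

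**Working it through.** The documents contain no figure to reproduce. The check is a comparison of texts, followed by one line of arithmetic.

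**Step 1: what the filter tests.** The test in SAP 10.1.1 is the date on which the AE begins. A later change in grade plays no part.

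**Step 2: which outputs carry the filter.**

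| Output | Onset filter stated? |
|---|---|
| Counts by maximum intensity (SAP 10.1.1) | Yes |
| Counts by strongest relationship (SAP 10.1.1) | By natural reading of the linking word; not restated |
| Incidence, intensity and relationship by System Organ Class and Preferred Term (opening of SAP 10.1.1) | No |
| Patients with AEs, total AEs, AEs associated with dosing, intensity (SAP 9.5) | No |
| AE incidence by group (SAP 10) | No |
| AEs leading to withdrawal (SAP 10.1.2) | No |
| SAEs (SAP 10.1.3) | No |
| General AE listing (Listing 16.2.8.1) | No |

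The problem is therefore confined to the first two rows.

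**Step 3: can a pre-dose AE exist in the data?** Yes. Protocol 6.2.2 collects wash-out AEs, and SAP 10.1.1 plans a listing for events that began before drug. The group is limited, because the wash-out is applied only where it is needed (Protocol 6.2.1 and the first footnote to the schedule in 6.1).

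**Step 4: which onset date does a worsened wash-out AE carry?** Two conventions are possible.

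- *One record, pre-dose onset.* Protocol 8.1 documents severity changes so that the duration at each intensity can be assessed, which describes one event passing through several grades. It asks for the onset and duration of each episode only for intermittent AEs. Under this convention the event fails the filter.
- *New record, dated from the deterioration.* Protocol 8.1 has a deteriorating pre-existing condition recorded as an AE. If that record is dated from the deterioration, and if a wash-out AE counts as pre-existing, the event passes the filter. But the rule is written for conditions entered under Medical History, and a wash-out event is collected as an AE.

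The first convention is the more natural reading. Neither is stated outright.

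**Step 5: size per patient.** Input: 30 patients planned per arm (Protocol 9.2, SAP 5), all assumed to be dosed and so in the Safety Population. One patient missing from a filtered count is 1/30 = 0.033, or 3.3 percentage points of that arm. This is a ceiling for a patient-based percentage in an arm of 30. SAP 10.1.1 counts each patient once per preferred term, so a patient with a separate on-drug episode of the same term is still counted.

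The documents give no rate of wash-out AEs or of their worsening, so no total can be computed.

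**The case against.** The strongest case on the other side is that no loss has been shown. The outcome depends on a CRF dating convention that the documents do not give, and under one of the two conventions nothing is lost. Even under the other, the event remains in the pre-dose listing and is summarised in several places without a filter. Protocol 8.2 treats a grade 3 gastrointestinal event as serious, so a wash-out symptom of that kind that reached grade 3 on drug would appear in the SAE summary, listing and narratives. All of this stands, and it limits the point to two sets of counts.

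Four stronger conclusions are tempting, and the documents do not support them:

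- *That such events disappear from the safety report.* They do not, for the reasons just given.
- *That the SAP contradicts Protocol 8.1.* Section 8.1 governs what is recorded, and the SAP sentence governs which records enter certain counts. Both can be followed. The mismatch is with the treatment-emergent endpoint in Protocol 3.4.
- *That the bias runs only against the active arms.* The filter also drops worsening on placebo. The comparison between arms is diluted only to the extent that worsening is more frequent on active drug.
- *That AE incidence in an active arm is understated by several multiples of 3.3 points.* No filter is stated for incidence, and nothing in the documents says how many patients would be affected.

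What the objection does not remove is that the SAP states an explicit rule, the rule omits worsening, and the endpoint it should serve is undefined.

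**Conclusion.** The point holds in limited form. As written, SAP 10.1.1 would leave a wash-out AE that worsens on drug out of the maximum-intensity counts, and by extension the strongest-relationship counts, if the event keeps its pre-dose onset date. That can understate on-drug severity and causality in those two outputs. It can also make outputs disagree: an event could appear in the SAE summary and be absent from the intensity counts.

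The size is at most 3.3 percentage points of an arm per affected patient, assuming 30 dosed patients per arm and a patient-based percentage. The number of patients is unknown and may be small. The conclusion rests on two readings: that the relationship counts inherit the filter, and that severity changes are kept within one AE record. The first is the natural reading. The second is the likelier one but is unstated. Under either dating convention the SAP needs an explicit rule before unblinding.

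**What to change.** In SAP 10.1.1, replace the inclusion sentence with a definition: a treatment-emergent AE is one that begins, or worsens in CTCAE grade, at or after the first dose, and the intensity tabulated is the maximum grade after the first dose. Apply it to the incidence, intensity and relationship tables in all four arms, placebo included, so that these outputs share one event set and match the endpoint in Protocol 3.4.

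State the CRF onset-date convention for worsening and align it with Protocol 8.1, saying whether an AE from the wash-out is treated as a pre-existing condition. The blinded data review planned in SAP 6.2 is a suitable point to confirm how such events were dated in practice.

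Keep the listing of events that began before dosing complete, and flag in it those that later worsened.

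The cost is a sentence or two in the SAP and one flag in a listing. No new data are needed, because Protocol 8.1 already requires severity changes to be documented.

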IL-1	Interleukin 1
IL-6	Interleukin 6
ITT	Intent to treat
LDL-C	Low density lipoprotein cholesterol
LVAD	Left ventricular assist device
MCH	Mean corpuscular hemoglobin

MCHC	Mean corpuscular hemoglobin concentration
MCV	Mean corpuscular volume
MedDRA	Medical Dictionary for Regulatory Activities
MI	Myocardial infarction
MTD	Maximum tolerated dose
NSCLC	Non-small cell lung cancer
PK	Pharmacokinetic
PR	Pulse rate
REC	Research ethics committee
RBC	Red blood cell
SAE	Serious adverse event
TC	Total cholesterol
TG	Triglycerides
TNF- α	Tumor necrosis factor alpha
ULN	Upper limit of normal range
US	United States
WBC	White blood cell

PROTOCOL SUMMARY

Title:	A Prospective, Double Blind, Randomized, Placebo-controlled Trial of Antroquinonol in Patients with Hypercholesterolemia and Hyperlipidemia
Study Phase:	Research (Phase II)
Sponsor:	Golden Biotechnology Corporation
Chief Principal Investigator:	[name]. [name]
Investigator:	National Taiwan University Hospital
Indication:	Hypercholesterolemia and Hyperlipidemia
Study product:	Antroquinonol (Hocena®)
Dose/Route:	Antroquinonol 150 mg, Antroquinonol 100 mg, Antroquinonol 50 mg, placebo, once daily/oral administration
Objectives:	The primary efficacy objective is to demonstrate the reduction of triglyceride (TG) by Antroquinonol, in comparison with placebo, after 12 weeks of treatment in patients with hypercholesterolemia and hyperlipidemia. Secondary objectives include the evaluation of the effects of Antroquinonol in comparison with placebo on other lipid parameters after 12 weeks of treatment and the effects of Antroquinonol on left ventricular diastolic function, arterial stiffness and fatty liver. The safety and tolerability of Antroquinonol will be monitored as well.
Population:	Patients with hypercholesterolemia and hyperlipidemia
Sample Size:	120 enrolments to achieve 96 completed subjects (drop-out rate: 20%)
Study Design:	A multi-center, prospective, double blind, randomized, placebo-controlled trial
Study Duration:	Approximately 24 months
Subject Participation Duration:	16 weeks including a two-week screening visit, a 12-week study treatment and a 2-week follow-up
	The end of the study is defined as all patients complete the

study treatment OR all patients are withdrawn and have been followed for two weeks, depending on which comes earlier.

Estimated Time for Recruitment:

The recruitment period of this study will be approximately 12 months.

Eligibility Criteria:Inclusion criteria:

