4.5.5. Handling of withdrawals

Subjects have the right to withdraw from the study at any time for any reason. The investigator also has the right to withdraw patients from the study in the event of intercurrent illness, adverse events, protocol violations, administrative reasons or other reasons. An excessive rate of withdrawals can render the study un-interpretable; therefore, unnecessary withdrawal of patients should be avoided. Should a patient decide to withdraw, all efforts will be made to complete and report the observations prior to withdrawal as thoroughly as possible.

The investigator should contact the subject or a responsible relative either by telephone or through a personal visit to establish as completely as possible the reason for the withdrawal. A complete final evaluation at the time of the subject's withdrawal should be made with an explanation of why the subject is withdrawing from the study. If the reason for removal of a subject from the study is an adverse event, the principal specific event will be recorded on the case report form (CRF).

Subjects withdrawing from the study should be followed for occurrence of adverse events unless the patient refuses to give further information.

Any subjects withdraw from the study, the study staff shall inform the sponsor and CRO within 5 working days.

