6.2.4. Final study visit (Day 99±3)

Safety Follow-Up Assessments at Visit 6 (± 3 days)

A safety follow-up for all patients will be conducted 2 weeks after the end of treatment visit.

The following assessments will be performed:

- Physical examination
- Anthropometric measures (Height, weight, waist circumference, BMI)
- Vital signs (pulse rate, body temperature, respiratory rate, and blood pressure)
- Blood samples for
 - lipid profile (total cholesterol, TG, HDL-C, LDL-C and LDL/HDL ratio)
 - hematology (WBC, RBC, Hb, Hct, RDW, platelet, MCV, MCH, MCHC, neutrophil-band and segment, lymphocyte, monocyte, eosinophil, basophil)
 - serum chemistry (AST, ALT, CPK, BUN, serum creatinine, albumin, total bilirubin, direct bilirubin, ALP, total protein)

- biomarkers (hsCRP, IL-1, IL-6, and TNF-alpha)
- Urinalysis
 - routine urine test (pH, protein, glucose, ketone, blood, urobilinogen, bilirubin, nitrite, leukocyte)
 - clinical microscopy
- Information on adverse events
- Information on new concomitant medications
- Provide final instructions to subject

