6.2.5. Early termination visit /Withdrawal visit

For subjects who prematurely withdraw from treatment, the same procedures as the one at the end of the treatment will be applied. An end of treatment visit should be scheduled as soon as possible and the assessments listed below should be performed. Subjects will be required to bring in all study drugs for assessment of compliance. If the decision of discontinuation is being taken while the subject is in the clinic for a visit, the end of treatment assessments may be performed on that day.

- Physical examination
- Anthropometric measures (Height, weight, waist circumference, BMI)
- Vital signs (pulse rate, body temperature, respiratory rate, and blood pressure)
- Blood samples for
 - lipid profile (total cholesterol, TG, HDL-C, LDL-C and LDL/HDL ratio)
 - hematology (WBC, RBC, Hb, Hct, RDW, platelet, MCV, MCH, MCHC, neutrophil-band and segment, lymphocyte, monocyte, eosinophil, basophil)
 - serum chemistry (AST, ALT, CPK, BUN, serum creatinine, albumin, total bilirubin, direct bilirubin, ALP, total protein)
 - biomarkers (hsCRP, IL-1, IL-6, and TNF-alpha)
- 12-lead electrocardiogram
- Brachial-ankle pulse wave velocity (baPWV) and ankle-brachial index (ABI)
- CT scan of the liver for patients with confirmed fatty liver at Visit 2
- Urinalysis
 - routine urine test (pH, protein, glucose, ketone, blood, urobilinogen, bilirubin, nitrite, leukocyte)
 - clinical microscopy
- Information on adverse events
- Information on new concomitant medications

A safety follow-up should be conducted for subjects who prematurely withdraw from treatment

2 weeks after the end of treatment visit. A clinic visit is recommended unless the subject refused to return. If so, the safety follow-up may be conducted via telephone.

Subjects willing to provide information should be followed for assessments of adverse events until the end of the trial. At a minimum, the investigator should make every effort to obtain information on whether or not the subject is alive or dead at the end of the study.

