7.6. Adverse event

The subject will be asked to report adverse event (AE) voluntarily and an investigator will also examine a subject for identifying adverse event at each visit during the study, starting from Visit 2 until the end of the trial. The methods and procedures for recording, assessing and reporting AEs are described in Section 8.

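### Adverse events are counted from first dose with no end date, while follow-up length differs between completers and withdrawn patients, so AE rates by arm depend on each arm's withdrawal rate

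*SAP*

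**What the plan says.** **Completers.** Under protocol 6.2.4, "A safety follow-up for all patients will be conducted 2 weeks after the end of treatment visit". This is Visit 6, Day 99 ± 3, the last column of the flow chart in 6.1. After a subject's final visit, protocol 8.4.1 asks for new SAEs to be recorded only if judged causally related.

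**Withdrawn patients.** Protocol 6.2.5 first sets a safety follow-up "2 weeks after the end of treatment visit. A clinic visit is recommended unless the subject refused to return". It then adds: "Subjects willing to provide information should be followed for assessments of adverse events until the end of the trial". Protocol 4.5.5 makes such follow-up subject to the patient's agreement: "Subjects withdrawing from the study should be followed for occurrence of adverse events unless the patient refuses to give further information".

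**End of the trial.** No date per subject is given. The Protocol Summary's definition opens with "The end of the study is defined as all patients complete the" and is framed in terms of all patients. Protocol 7.6 uses similar words for every subject: AEs are sought at each visit, "starting from Visit 2 until the end of the trial".

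**Censoring.** Protocol 9.5 censors values measured after early termination of study drug. Neither document says whether this covers AEs.

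**Counting.** SAP 10.1.1 states "Only AEs beginning at or after the beginning of study drug administration will be included" and gives no end. It counts a patient once per preferred term within a study period that it does not define for AEs. It also specifies a test: "Fisher's exact test will be used to compare rates for System Organ Classes across treatment groups". Protocol 3.4 names the incidence of treatment-emergent AEs as a safety endpoint, again without a window.

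**The concern.** A crude incidence, meaning patients with at least one event divided by patients treated, is comparable across arms only if patients are observed for similar lengths of time. Here the observation time depends on whether a patient completes, and withdrawal is an outcome of treatment that may differ by arm. An AE months after a patient stopped drug can count for that arm, while the same AE in a completer after Day 99 has no scheduled enquiry to capture it. If withdrawn patients are instead counted only briefly after stopping, the arm with more withdrawals is under-observed.

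Safety and tolerability against placebo is a stated objective (protocol 2.2), and tolerability is a safety endpoint (protocol 3.4, SAP 3.2.3). The incidence, intensity and relationship tables and the Fisher tests all inherit the problem. Because the plan does not settle the window, two programmers could produce different AE tables from the same data, and the choice could be made after unblinding.

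**Working it through.** **The plan's own time frame.** Screening, treatment and follow-up give (14 + 84 + 14)/7 = 16 weeks, as the Protocol Summary states. Day 85 + 14 = Day 99, so a completer is observed for 98 days from first dose, or 98/30.44 = 3.22 months.

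**Inputs from the documents.** Recruitment lasts about 12 months and planned drop-out is 20% (Protocol Summary, 9.2). Study end is taken as the last patient's completion of treatment, 84 days (2.76 months) after the last entry.

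**Assumptions, none given in the documents.** Entry is uniform over 12 months. The AE rate is constant and equal in every arm at 0.1 per month, on or off drug. Withdrawal occurs at week 6, in 10% of one arm and 40% of another.

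**Formulas.** The probability of at least one AE in t months is F(t) = 1 − exp(−0.1t). Arm incidence is (1 − w) × F(completer) + w × F(withdrawn), where w is the withdrawal proportion.

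- Completer: F(3.22) = 27.5%.
- Withdrawn, followed to study end: t is uniform from 2.76 to 14.76 months, mean 8.76. Average F = 1 − [exp(−0.276) − exp(−1.476)]/1.2 = 1 − (0.7588 − 0.2286)/1.2 = 55.8%.
- Withdrawn, counted to two weeks after stopping: t = 56 days = 1.84 months, F = 16.8%.
- Withdrawn, cut at drug stop (9.5 applied to AEs): t = 42 days = 1.38 months, F = 12.9%.

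| Reading for withdrawn patients | 10% withdrawn | 40% withdrawn | Difference |
|---|---|---|---|
| All followed to study end | 30.4% | 38.8% | +8.5 |
| Half to study end, half to two weeks | 28.4% | 31.0% | +2.6 |
| All to their own planned Day 99 | 27.5% | 27.5% | 0 |
| All to two weeks after stopping | 26.5% | 23.2% | −3.2 |
| All cut at drug stop | 26.1% | 21.7% | −4.4 |

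For example, the top row is 0.9 × 27.5 + 0.1 × 55.8 = 30.4 (unrounded inputs) and 0.6 × 27.5 + 0.4 × 55.8 = 38.8.

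**Break-even.** If the rest are counted to two weeks, the sign turns positive once the share accepting follow-up to study end exceeds (27.5 − 16.8)/(55.8 − 16.8) = 27%. Over rates of 0.5 to 4 per patient-year, with study end taken at the last patient's Day 99, this share runs from about 22% to 44%.

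**Other rates.** At 0.05 and 0.2 per month, the study-end reading gives +5.9 and +9.2 points. The two-week reading gives −1.8 and −5.0.

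**Share of follow-up time.** At the planned 20% drop-out with all followed to study end, withdrawn patients supply 0.2 × 8.76/(0.2 × 8.76 + 0.8 × 3.22) = 40% of AE follow-up time.

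**The case against.** A reader might infer that AE rates must rise with withdrawal, and so that the tables will show a false dose-related excess. The documents do not support that.

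- **The phrase is ambiguous.** Protocol 7.6 applies the same end-of-trial wording to all subjects, and 4.4 fixes participation at 16 weeks. If each subject's own end is meant, there is no imbalance. Against this, the sentence in 6.2.5 comes after the two-week follow-up and so appears to add to it, and 7.6 ties enquiry to visits, of which completers have none after Visit 6. The study-level reading is the more natural one, but it is not certain.
- **Follow-up is voluntary.** It depends on willingness (4.5.5, 6.2.5), the withdrawal reasons in 4.5.4 include withdrawn consent and loss to follow-up, and no contact schedule exists beyond two weeks. With few willing, the sign reverses.
- **Censoring under 9.5** may or may not reach AEs. If it does, the imbalance also reverses.
- **No dose gradient is documented.** The 10% versus 40% split is an assumption. The gastrointestinal rates in 8.2 are attributed only to clinical trials in general, and the earlier trial described in 1.3.1 is a Phase I dose-finding study in lung cancer. Withdrawal for lack of response (4.4, 4.5.4) could instead concentrate on placebo.
- **The effect is modest.** With 30 per arm, the standard error of a difference such as 30% versus 39% is about 12 points. A 10-point gap in withdrawal gives at most 0.1 × (55.8 − 27.5) = 2.8 points at 0.1 per month, under one patient in 30. Fisher's test is specified for System Organ Classes, not for the any-AE rate used here.

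Two details carry no weight. Assigning AEs to the most recent treatment changes nothing in a parallel trial with one treatment per patient. The sentence giving the start of counting stands in the paragraph on maximum intensity. The separate listing of pre-dose AEs suggests it is meant generally, and if it is not, the incidence tables have neither a start nor an end.

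All of this limits the direction and size. It does not supply the missing end date.

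**Conclusion.** The point holds in this form: the plan compares crude AE incidence across arms over observation windows that depend on completion status, with no end date, so AE rates by arm depend on withdrawal rates. The direction is not determined by the documents. Under the stated assumptions (equal AE rate of 0.1 per month, uniform 12-month entry, withdrawal at week 6, 10% versus 40%), the spurious difference runs from about −3 points with two-week counting to about +8 with all followed to study end, and to about −4 if 9.5 censoring covers AEs. Only follow-up of every withdrawn patient to their own planned Day 99 makes it vanish, and neither document states that rule. This is worth correcting before unblinding. It is not evidence that the trial will show a false dose effect.

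**What to change.** 1. Reconcile protocol 6.2.5, 7.6, 8.4.1 and 9.5 on the AE collection period, and state whether the 9.5 censoring covers AEs.
2. In SAP 10.1.1 and Tables 14.4.8.1 and 14.4.8.2, count in the comparative incidence, intensity and relationship tables and in the Fisher tests only AEs with onset from first dose to planned Day 99, for every patient, on or off drug.
3. Show observed patient-time per arm beside the counts. Beyond the two-week contact, 6.2.5 depends on willingness, so patients who decline remain under-observed and the common cut-off reduces the bias without removing it.
4. List later AEs separately. In SAP 10.1.3, keep all SAEs, including later related ones, in the summary and flag late onset. SAP 10.1.2 needs no change, since AEs leading to withdrawal start before it.

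The cost is the protocol clarification, a sentence or two in the SAP, one onset-date filter and a patient-time row. The downside is that late non-serious events in withdrawn patients move from tables to a listing.
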